4.6.5.5. Immunogenicity

4.6.5.5.1. Definitions of Sample ADA Status

At a high level, an individual sample is potentially examined multiple times, in a hierarchical procedure, to produce a sample ADA assay result and potentially multiple cross-reactive antibodies assay results and multiple NAb assay results. The cut points used, the drug tolerance of each assay, and the possible values of titers are operating characteristics of the assay.

Figure GPHN.4.1 details a flow chart that reflects the multitiered testing approach.

Abbreviations: ADA = anti-drug antibodies; CP = cut point; GIPR = glucose-dependent insulinotropic polypeptide receptor; GLP-1R = glucagon-like peptide-1 receptor; LY = LY3298176 (tirzepatide); NAb = neutralizing antibody; nGIP = native glucose-dependent insulinotropic polypeptide; nGLP-1 = native glucagon-like peptide-1.

Figure GPHN.4.1. Flowchart of immunogenicity multitiered testing approach.

Table GPHN.4.7 outlines results as reported from Tier 2a of the multitiered testing approach. Tier 4 results are reported similarly.

Table GPHN.4.7. Sample ADA Assay Results

Sample Laboratory Result	Explanation
Detected	ADA are detected and confirmed.
Not Detected	The raw result as reported from the laboratory indicates not detected. The clinical interpretation of such results depends on other factors (see Table GPHN.4.8).
NO TEST, QNS, etc.	Sample exists but was unevaluable by the assay.

Abbreviations: ADA = anti-drug antibodies; QNS = quantity not sufficient.

It can be the case that the presence of high concentrations of tirzepatide will affect ADA immunoassays, and conversely high levels of antibodies may affect the measurement of tirzepatide concentration. Thus, a tirzepatide drug concentration, assessed from a sample drawn at the same time as the ADA sample, plays a key role in clinical interpretation of a sample when the laboratory result is Not Detected (see [Table GPHN.4.8](#)).

Table GPHN.4.8. Sample Clinical ADA Interpretation Results

Sample Clinical Interpretation	Explanation
ADA Present	ADA assay result is Detected
ADA Not Present	
ADA assay result is Not Detected and simultaneous drug concentration is at a level that has been demonstrated to not interfere in the ADA detection method (ie, drug concentration is below the assay's drug tolerance level).
 
For participants receiving placebo, drug concentration is not assessed and is assumed to be below the assay's drug tolerance level.
 
If drug concentration was planned but is not available for a treatment-period sample, a Not Detected sample will be declared ADA Not present.

ADA Inconclusive	ADA assay result is Not Detected but drug concentration in the sample is \geq the assay's drug tolerance level, which may cause interference in the ADA detection method.

Abbreviation: ADA = anti-drug antibodies.

All ADA present samples will be evaluated for cross-reactivity to native GIP (Tier 2b), cross-reactivity to native GLP-1 (Tier 2c), NAb LY (tirzepatide) on GIPR (Tier 4a), and NAb LY (tirzepatide) on GLP-1R (Tier 4b). If cross-reactive ADA against native GIP is detected, the *in silico* assessment for cross-reactive NAb against native GIP is evaluated. If cross-reactive ADA against native GLP-1 is detected, the *in silico* assessment for cross-reactive NAb against native GLP-1 is evaluated ([Figure GPHN.4.1](#)).

Similar terminology to [Table GPHN.4.8](#) applies for each type of cross-reactive and NAb assay. Importantly, each of these are distinct assays and, in general, have different assay operating characteristics.

The following are considered inconclusive for the NAb result:

- NAb LY on GIPR: if NAb result is not detected, and PK concentration is \geq drug tolerance limit of the NAb LY on GIPR assay
- NAb LY on GLP-1R: if NAb result is not detected, and PK concentration is \geq drug tolerance limit of the NAb LY on GLP-1R assay

To mitigate inconclusive cross-reactive neutralizing antibody interpretations against native GIP and GLP-1 due to potential tirzepatide concentrations above the drug tolerance limit of the NAb GIP on GIP-R (Tier 4c) and NAb GLP-1 on GLP-1R (Tier 4d) assays.

An *in silico* method utilizing results from Tiers 2b and 2c, Tiers 4a and 4b, and tirzepatide concentrations is used to determine cross-reactive NAb against native GIP and GLP-1. The *in silico* method is outlined in the following table:

Table GPHN.4.9. In Silico Classification for Cross-Reactive NAb

In Silico Classification	Cross-Reactive ADA Result	NAb Result	Circulating Tirzepatide Level (ng/mL)	In Silico Cross- Reactive NAb Interpretation
Cross-Reactive NAb to nGIP	Tier 2b: “Not Detected” Tier 2b: “Detected” Tier 2b: “Detected” Tier 2b: “Detected”	Tier 4a: “Not Detected” Tier 4a: “Detected” or N/A or Missing Tier 4a: “Not Detected” Tier 4a: “Detected” Tier 4a: “Detected”	Any value or missing or $<$ drug tolerance limit of Tier 4a assay \geq drug tolerance limit of Tier 4a assay $<$ drug tolerance limit of Tier 4a assay \geq drug tolerance limit of Tier 4a assay	Not Present Not Present Inconclusive Present Present
Cross-Reactive NAb to nGLP-1	Tier 2c: “Not Detected” Tier 2c: “Detected” Tier 2c: “Detected” Tier 2c: “Detected”	Tier 4b: “Not Detected” Tier 4b: “Detected” or N/A or Missing Tier 4b: “Not Detected” Tier 4b: “Detected”	Any value or missing or $<$ drug tolerance limit of Tier 4b assay \geq drug tolerance limit of Tier 4b assay $<$ drug tolerance limit of Tier 4b assay	Not Present Not Detected Inconclusive Detected

In Silico Classification	Cross-Reactive ADA Result	NAb Result	Circulating Tirzepatide Level (ng/mL)	In Silico Cross- Reactive NAb Interpretation
	Tier 2c: "Detected"	Tier 4b: "Detected"	≥ drug tolerance limit of Tier 4b assay	Detected

Abbreviations: ADA = anti-drug antibodies; NAb = neutralizing antibody; nGIP = native glucose-dependent insulinotropic polypeptide; nGLP-1 = native glucagon-like peptide-1; Tier 2b = cross-reactive ADA to nGIP; Tier 4a = NAb LY (tirzepatide) on GIPR; Tier 4b = NAb LY (tirzepatide) on GLP-1R.

Note that in the case of an ADA Inconclusive sample, each of the NAb and Cross-Reactive NAb assay results is taken to be Inconclusive.

Note also that any reference to an assay cut point and/or drug tolerance is population specific, and is subject to modification to study-specific parameters per regulatory guidance.

4.6.5.5.2. Definitions of Immunogenicity Assessment Periods

Immunogenicity Baseline Observations: Baseline period for immunogenicity assessment for each participant includes all observations prior to first dose of study treatment. In instances where multiple baseline observations are collected, to determine participant ADA status the last nonmissing immunogenicity assessment prior to first administration of study drug is used to determine treatment-emergent status (see below).

Immunogenicity Postbaseline Period Observations: Postbaseline period observations for each participant includes all observations after the first administration of study drug. There are 2 different periods listed below:

- The planned treatment period is defined as from the first dose of treatment to end of the treatment period.
- The entire postbaseline period is defined as from the first dose of treatment to the end of safety follow-up visit or date of study withdrawal

4.6.5.5.3. Definitions of Participant ADA Status

Participant evaluable for TE ADA: a participant has a nonmissing baseline ADA result, and at least 1 nonmissing postbaseline ADA result.

Treatment-emergent ADA-unevaluable participant: any participant who does not meet the evaluable criteria.

Baseline ADA Present (preexisting antibody): ADA detected in a sample collected up to the first dose date and time.

Baseline ADA Not Present: ADA is not detected, and the corresponding PK concentration is missing or below the drug tolerance limit in a sample collected up to the first dose date and time.

Treatment-emergent ADA positive (TE ADA+) participant: A participant who is evaluable for TE ADA is TE ADA+ if either of the following holds:

- The participant has baseline status of ADA Not Present and at least 1 postbaseline status of ADA Present with titer $\geq 2 \times$ MRD of the ADA assay.
- The participant has baseline and postbaseline status of ADA Present, with the postbaseline titer being 2 dilutions (4-fold) greater than the baseline titer. That is, the participant has baseline (B) status of ADA Present, with titer 1:B, and at least 1 postbaseline (P) status of ADA Present, with titer 1:P, with P/B ≥ 4 .

As shown in [Figure GPHN.4.1](#), a titer is expected when ADA assay result is detected. On occasion, the corresponding assay cannot be performed, in which case a titer value will be imputed for the purpose of TE ADA determination. A baseline sample with detected ADA and no titer is imputed to be the MRD (1:10), and a postbaseline sample with ADA detected and no titer is imputed to be 1 dilution above the MRD (1:20).

Treatment-emergent ADA inconclusive participant: A TE ADA-evaluable participant is TE ADA inconclusive if $\geq 20\%$ of the participant's postbaseline samples are ADA inconclusive and all remaining postbaseline samples are ADA not present.

Treatment-emergent ADA negative (TE ADA-) participant: A TE ADA evaluable participant is TE ADA- when the participant is not TE ADA+ and not TE ADA inconclusive.

For each NAb assay, the following are defined:

NAb-positive (NAb+) participant: A participant who is TE ADA+ and has a NAb+ sample in the postbaseline period.

NAb-inconclusive participant: A participant who is TE ADA+, is not NAb+, and all samples that have TE ADA+ titer have a NAb-inconclusive sample result.

NAb-negative (NAb-) participant: A participant who is neither NAb+ nor NAb inconclusive.

Unless specified otherwise, the above-mentioned definitions of NAb are applicable to all NAb analyses, including cross-reactive NAb analyses, and cross-reactive antibodies.

4.6.5.5.4. Analyses to be Performed

Two analysis sets will be considered:

- mITT analysis set: refer to Section 3. Note that for mITT population, only time during tirzepatide exposure will be summarized.
- For participants who randomized to tirzepatide MTD arm.

The analysis period was defined in Section [4.6.5.5.2](#). The count and proportion of participants who are TE ADA+ will be tabulated, where proportion are relative to the number of participants who are TE ADA evaluable, as defined above. The tabulation will include the number and proportion of participants with ADA Present at baseline, and the number and proportion of TE ADA+ participant exhibiting each type of cross-reactive antibodies and NAb. *In silico* classification for cross-reactive NAb will be summarized.

A summary will be provided of the count and percentage of tirzepatide-treated participants experiencing specific TEAE (see [Table GPHN.4.10](#)) by participant TE ADA status (TE ADA+, TE ADA-, TE ADA inconclusive) during the planned treatment period.

Table GPHN.4.10. Adverse Events for Analysis with Immunogenicity Results

TEAE category	Criteria
Hypersensitivity reactions	Anaphylactic reaction SMQ (narrow or algorithm)
	Hypersensitivity SMQ (narrow)
	Angioedema SMQ (narrow)
	Severe Cutaneous Adverse Reaction SMQ (narrow)
	Vasculitis SMQ (narrow)
Injection site reactions	Injection site reaction HLT
	Infusion site reaction HLT
	Administration site reaction HLT

Abbreviations: HLT = High Level Term; MedDRA = Medical Dictionary for Regulatory Activity; SMQ = Standardized MedDRA Query; TEAE = treatment-emergent adverse event.

A listing will be provided for all participants who had ADA Present at any time (including baseline) or had any specific TEAE (see [Table GPHN.4.10](#)). This listing includes a time course of ADA (clinical interpretation result plus flags for samples meeting TE ADA+ criteria and for samples with cross-reactive antibodies and NAb present) along with the TEAE.

Cases of TE ADA that are associated with AEs of either severe/serious hypersensitivity or severe/serious ISR will be classified as AESIs.

Additional immunogenicity analyses as determined later may be presented. The relationship between antibody titers, the PK parameters, and PD response to tirzepatide may also be assessed.

4.6.5.6. Hypersensitivity Reactions

Two main analyses are performed in support of assessment of potential immediate hypersensitivity, including anaphylaxis, and as well as potential non-immediate hypersensitivity.

Time Period A, of potential immediate hypersensitivity, includes all TEAEs occurring from start of study drug administration up to 24 hours after end of study drug administration. For events without the hypersensitivity eCRF, only date (no time) information is collected; if such events occurred on the same date as the study drug injection date, they will be included in Time Period A.

Time Period B, of potential non-immediate hypersensitivity, includes all TEAEs occurring more than 24 hours after the end of study drug administration, but prior to subsequent drug administration.

The counts and percentages of participants who experienced a hypersensitivity TEAE will be summarized by PT with decreasing frequency by treatment.

Analyses for both time periods are based on the following:

- Narrow and algorithm terms in Anaphylactic reaction standardized MedDRA query (SMQ) (20000021) (Note that Anaphylactic reaction SMQ algorithm will only be summarized for Time Period A)
- Narrow terms in Angioedema SMQ (20000024)
- Narrow terms in Severe cutaneous adverse reactions SMQ (20000020)

- Narrow terms in Hypersensitivity SMQ (20000214), and
- Narrow terms in Vasculitis SMQ (20000174)

Additionally, for the Anaphylactic reaction SMQ in Time Period A, the algorithmic query (per the MedDRA Maintenance and Support Services Organization SMQ guide) will be performed. An algorithmic case must include either:

- A narrow term from the SMQ (Category A of the SMQ);
- Multiple terms from the SMQ, from the same administration of study drug, comprising terms from at least 2 of the following categories from the SMQ:
 - Category B - (Upper Airway/Respiratory)
 - Category C - (Angioedema/Urticaria/Pruritus/Flush)
 - Category D - (Cardiovascular/Hypotension)

Where algorithm is mentioned below, this applies only to Time Period A.

The counts and percentages of participants who experienced a TEAE for the following will be analyzed for each of the 2 time periods:

- Any narrow or algorithm term from any 1 of the 5 SMQs indicated above (ie, combined search across narrow and algorithmic portions of all 5 SMQs)
- Any narrow or algorithm term within each SMQ, separately (ie, narrow SMQ search).

Within query, individual PTs that satisfied the queries will be summarized. For Time Period A analysis, the Anaphylactic reaction SMQ algorithm will be summarized. Also, a single event may satisfy multiple SMQs, in which case the event contributes to every applicable SMQ.

4.6.5.6.1. Severe/Serious Hypersensitivity Reactions

The severe/serious cases of hypersensitivity will be considered as AESIs. Summary with severe/serious hypersensitivity reactions may be provided, if deemed necessary.

4.6.5.7. Injection Site Reaction

Injection site reaction, incidence and rates, and related information reported via “Injection Site Reactions” eCRF will be summarized by treatment. Information to be summarized includes location of the reaction, timing of reaction relative to study drug administration, and characteristics of the injection site reaction: erythema, induration, pain, pruritus, and edema.

Patient-based analysis and event-based analysis may be provided if necessary. The patient-based analysis summarizes all ISR questionnaire forms for an individual participant with a single statistic, typically an extreme value. This analysis allows each participant to contribute only once for each parameter, at the expense of a focus on the most extreme events. By contrast, the event-based analysis summarizes all ISR questionnaire forms received, without regard to individual participants. This provides characteristics of ISR events as a proportion of all events for which questionnaire responses were provided, at the expense of some potential bias due to differential contribution of individual participants to the analysis.

The counts and percentages of participants with treatment-emergent injection site reaction will be summarized by treatment using the MedDRA PTs. Detailed searching criteria can be found in [Appendix 7](#).

The PT will be summarized within each category in decreasing order of incidence for tirzepatide-treated participants.

4.6.5.7.1. *Severe/Serious Injection Site Reactions*

The severe/serious treatment-emergent injection site reactions based on TEAE search criteria specified in [Appendix 7](#) will be considered as AESIs. The counts and percentages of participants with severe/serious injection site reactions will be summarized by treatment. A listing of participants with treatment-emergent severe/serious ISRs may be provided, if deemed necessary.

4.6.5.8. *Major Adverse Cardiovascular Events*

The following positively adjudicated MACE will be considered as AESI:

- death due to cardiovascular AEs
- myocardial infarction
- hospitalization for unstable angina
- hospitalization for heart failure
- coronary interventions (such as coronary artery bypass graft or percutaneous coronary intervention), and
- cerebrovascular events, including cerebrovascular accident (stroke) and transient ischemic attack.

The counts and percentages of participants with positively adjudicated MACE may be summarized by treatment.

A listing of participants reporting MACE events, either reported by investigator or identified by the Clinical Evaluation Committee, may be provided.

In addition, MACE reported by investigator may be summarized although a MACE reported by investigator and not positively adjudicated is not considered as AESI.

4.6.5.9. *Major Depressive Disorder / Suicidal Ideation or Behavior*

The severe/serious major depressive disorder/suicidal ideation or behavior will be captured as AESI. Adverse events will be searched using MedDRA PT terms. Detailed searching criteria can be found in [Appendix 7](#).

The counts and percentages of participants with TEAEs will be summarized by treatment group using MedDRA PT nested within SMQ. Events will be ordered by decreasing frequency nested within SMQ. A listing of participants with major depressive disorder/suicidal ideation or behavior may be provided if deemed necessary.

In addition to spontaneously reported AEs assessed by the investigator, suicidal ideation and behavior and depression will be assessed through the use of the C-SSRS and the PHQ-9, respectively.

4.6.5.9.1. *Patient Health Questionnaire*

Total scores for the PHQ-9 range from 0 to 27 with total scores being categorized as follows:

- None (not depressed) 0 – 4

- Mild 5 – 9
- Moderate 10 – 14
- Moderately Severe 15 – 19, and
- Severe 20 – 27.

Shift tables will be provided showing the counts and percentages of participants within each baseline category (maximum value) versus each postbaseline category (maximum value) by treatment.

Additionally, the following 3 outcomes of interest will be compared between treatments (based on the maximum value during baseline and postbaseline):

- Any increase in depression category (ie, worsening of depression); includes participants in the none, mild, moderate, or moderately severe category during baseline and with at least 1 postbaseline measurement;
- Increase from No or Mild Depression to Moderate, Moderately Severe, or Severe Depression; includes participants in the none or mild depression category during baseline and with at least 1 postbaseline measurement; and
- Increase from Mild or Moderate Depression to Moderately Severe or Severe Depression; includes participants in the mild or moderate depression category during baseline and with at least 1 postbaseline measurement.

4.6.5.9.2. Suicidal Ideation and Behavior Solicited Through C-SSRS

Suicide-related thoughts and behaviors occurring during the double-blind study period, based on the C-SSRS, will be summarized by treatment group. In particular, for each of the following suicide-related events, the counts and percentages of participants with the event will be summarized by treatment group:

- Died by suicide
- Nonfatal suicide attempt
- Interrupted attempt
- Aborted attempt
- Preparatory acts or behavior
- Active suicidal ideation with specific plan and intent
- Active suicidal ideation with some intent to act without specific plan
- Active suicidal ideation with any methods (no plan) without intent to act
- Nonspecific active suicidal thoughts
- Wish to be dead, and
- Non-suicidal, self-injurious behavior.

In addition, the counts and percentages of participants who experienced at least 1 of the composite measures will be presented. The participants with at least 1 postbaseline C-SSRS assessment are included. The composite measure is determined at each assessment by the “yes” or “no” responses in C-SSRS categories by the study participant:

- Category 1 – Wish to be Dead

- Category 2 – Non-specific Active Suicidal Thoughts
- Category 3 – Active Suicidal Ideation with Any Methods (Not Plan) without Intent to Act
- Category 4 – Active Suicidal Ideation with Some Intent to Act, without Specific Plan
- Category 5 – Active Suicidal Ideation with Specific Plan and Intent
- Category 6 – Preparatory Acts or Behavior
- Category 7 – Aborted Attempt
- Category 8 – Interrupted Attempt
- Category 9 – Actual Attempt (non-fatal), and
- Category 10 – Completed Suicide.

Composite endpoints of suicidal ideation and suicidal behavior based on the above categories are defined below:

- **Suicidal ideation:** A “yes” answer at any time during the double-blind treatment period of the study to any 1 of the 5 suicidal ideation questions (Categories 1 – 5) on the C-SSRS
- **Suicidal behavior:** A “yes” answer at any time during double-blind treatment period of the study to any 1 of the 5 suicidal behavior questions (Categories 6 – 10) on the C-SSRS, and
- **Suicidal ideation or behavior:** A “yes” answer at any time during double-blind treatment period of the study to any 1 of the 10 suicidal ideation and behavior questions (Categories 1 – 10) on the C-SSRS.

A listing containing data for each participant with suicidal ideation, suicidal behavior, or non-suicidal self-injurious behavior during the double-blind treatment period of the study by treatment and visit may be provided. Data from all visits are displayed, regardless of a “yes” or “no” answer, for participants with any “yes” answer for suicidal ideation, suicidal behavior, or self-injurious behavior without suicidal intent.

4.6.5.10. Malignancy

Malignancy will be considered as AESI. The counts and percentages of participants with treatment-emergent malignancy will be summarized by treatment and PT ordered by decreasing frequency. Detailed searching criteria can be found in [Appendix 7](#).

4.6.5.11. Renal Safety

Laboratory measures related to renal safety will be analyzed as specified for laboratory measurements in Section [4.6.3.3](#).

Additionally, 2 shift tables examining renal function will be created. A min-to-min shift table of estimated glomerular filtration rate estimated by the Chronic Kidney Disease Epidemiology Collaboration equation with units mL/min/1.73m², using categories (<30, ≥30 to <45, ≥45 to <60, ≥60 to <90, and ≥90 mL/min/1.73m²). A max-to-max shift table of UACR, using the categories UACR<30 mg/g, 30 mg/g ≤UACR≤300 mg/g, UACR>300 mg/g (respectively, these represent normal, microalbuminuria, and macroalbuminuria).

Mixed model repeated measure analyses for estimated glomerular filtration rate and UACR will be provided. Log transformation will be performed for UACR.

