EQ-5D-5L		X								X															X		X
Mental Health Questionnaires																											
PHQ-9	X	X			X			X		X				X			X		X		X		X		X	X	X
	PHQ-9 is self-administered and should be completed after assessment of adverse events.																										
C-SSRS (Baseline/Screening Version)	X																										
	The C-SSRS should be administered after assessment of adverse events. For this study, the C-SSRS is adapted for the assessment of the ideation and behavior categories only. The Intensity of Ideation and Lethality of Behavior sections are removed.																										
C-SSRS (Since Last Visit Version)		X	X	X	X	X	X	X	X	X	X	X	X	X	X	X	X	X	X	X	X	X	X	X	X	X	
	The C-SSRS should be administered after assessment of adverse events and capture information since most recent C-SSRS administration. For this study, the C-SSRS is adapted for the assessment of the ideation and behavior categories only. The Intensity of Ideation and Lethality of Behavior sections are removed.																										
Self-Harm Supplement Form	X	X	X	X	X	X	X	X	X	X	X	X	X	X	X	X	X	X	X	X	X	X	X	X	X	X	
	The Self-Harm supplement form should be administered after assessment of adverse events.																										

Visit	1	2	3	4	5	6	7	8	9	10	11	12	13	14	15	16	17	18	19	20	21	22	23	24	99	ED	801	
Week of Treatment	-2	0	4	8	12	16	20	24	28	32	36	40	44	48	52	56	60	64	68	72	76	80	84	88	88		4 wks post end of TxP	
Allowable Interval Tolerance (days)		±3	±3	±3	±3	±3	±3	±3	±3	±3	±3	±3	±3	±3	±3	±3	±3	±3	±3	±3	±3	±3	±3	±3	±7	±7	±3	
Fasting Visit	X	X	X	X	X	X	X	X	X	X	X	X			X		X		X		X		X	X	X	X		
Telephone Visit													X	X		X	X		X	X		X	X					
Self-Harm Follow-up Form	X	X	X	X	X	X	X	X	X	X	X	X	X	X	X	X	X	X	X	X	X	X	X	X	X	X		
	Self-Harm Follow-up Form is only required if triggered by the Self-Harm Supplement Form, per instructions in the form.																											
Laboratory Tests and Sample Collections																												
Hematology	X				X			X			X														X		X	
HbA1c	X	X			X			X			X				X			X			X			X		X	X	
Chemistry panel (includes Cr for eGFR calculation and glucose)	X	X			X			X			X				X			X			X			X		X	X	
	The CKD-EPI equation will be used by the central lab to estimate and report eGFR.																											
Insulin		X			X			X			X				X			X			X			X		X	X	
C-peptide		X			X			X			X				X			X			X			X		X	X	
Lipid panel	X	X						X			X														X		X	X
Free fatty acids	X	X						X			X														X		X	X

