### **8.3.2.12. Acute Renal Events**

Renal safety will be assessed based on repeated renal function assessment, as well as assessment of AEs suggestive of acute or worsening of chronic renal failure. Gastrointestinal AEs have been reported with tirzepatide, including nausea, diarrhea, and vomiting. This is consistent with other GLP-1R agonists (Aroda and Ratner 2011). The events may lead to dehydration, which could cause a deterioration in renal function, including acute renal failure. Participants should be advised to notify investigators in case of severe nausea, frequent vomiting, or symptoms of dehydration.

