### 9.2. Sample Size Determination

Approximately 1000 participants will be screened and 750 participants enrolled into the 36-week open-label tirzepatide lead-in treatment period in order to get approximately 600 participants to be randomized in a 1:1 ratio to tirzepatide MTD (300 participants) or placebo (300 participants).

The sample size determination assumes that evaluation of superiority of tirzepatide MTD to placebo will be conducted at a 2-sided significance level of 0.05 using a 2-sample t-test.

Additionally, a difference of at least 6% mean body weight percentage change from randomization (36 weeks) to 88 weeks between tirzepatide MTD and placebo, a common SD of 8%, and a dropout rate of 25% are assumed for statistical power calculations. Under the assumptions above, randomizing 600 participants in a 1:1 ratio to tirzepatide MTD (300 participants) and placebo (300 participants) provides more than 90% power to demonstrate superiority of tirzepatide MTD to placebo.

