**Calculationsa**

eGFR (calculated by CKD-EPI equation)  
UACR

Abbreviations: ALT = alanine aminotransferase; AST = aspartate aminotransferase; BUN = blood urea nitrogen; CKD-EPI = Chronic Kidney Disease-Epidemiology; eGFR = estimated glomerular filtration rate; EDTA = ethylenediaminetetraacetic acid; HbA1c = hemoglobin A1c; HDL-C = high-density lipoprotein cholesterol; LDL-C = low-density lipoprotein cholesterol; RBC = red blood cells; UACR = urine albumin to creatinine ratio; VLDL-C = very low-density lipoprotein cholesterol; WBC = white blood cells.

- a All tests will be performed by a Lilly-designated central laboratory, unless otherwise noted.
- b Results will not be provided to the investigative sites.
- c This value will be calculated. If triglycerides are  $>400$  mg/dL, the direct LDL will be assayed.

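### The planned eGFR comparisons use creatinine only, in arms planned to diverge in weight; cystatin C is collected, but the SAP specifies no eGFR from it

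*SAP*

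**What the plan says.** - **Planned eGFR analyses.** SAP 4.6.5.11 (Renal Safety) specifies "A min-to-min shift table of estimated glomerular filtration rate estimated by the Chronic Kidney Disease Epidemiology Collaboration equation", with five categories cut at 30, 45, 60 and 90 mL/min/1.73 m², and a mixed model for repeated measures of eGFR. It names neither the filtration marker nor the version of the equation.
- **Marker.** The laboratory row of the Schedule of Activities (protocol 1.3) reads "Chemistry panel (includes Cr for eGFR calculation and glucose" and is followed by "The CKD-EPI equation will be used by the central lab to estimate and report eGFR". The calculated values in protocol Appendix 2 are eGFR and UACR only.
- **Cystatin C.** Protocol 1.3 schedules it and Appendix 2 lists it as a central laboratory test. The SAP does not mention it.
- **Planned divergence.** Protocol 9.2, repeated in SAP 5, assumes "a difference of at least 6% mean body weight percentage change from randomization (36 weeks) to 88 weeks between tirzepatide MTD and placebo".
- **Role of renal function.** Protocol 8.3.2.12 says "Renal safety will be assessed based on repeated renal function assessment", and in the same sentence adds adverse events suggesting acute or worsening chronic renal failure. It gives dehydration from gastrointestinal events as the route of concern.
- **Other renal analyses.** SAP 4.6.5.11 also plans a max-to-max UACR shift table and a log-scale UACR model. SAP 4.6.5.11.1 and 4.6.5.11.2 plan event searches for acute renal failure, chronic kidney disease and dehydration, with severe or serious cases treated as events of special interest.

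**The concern.** A creatinine-based estimate moves with creatinine generation as well as with filtration, and generation is taken here to follow lean mass. In most trials randomization keeps that balanced. Here the weight difference is the intended treatment effect and develops after Week 36. If some of it is lean tissue, the arms would differ in creatinine eGFR with identical filtration.

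The direction matters for a safety analysis: the artefact raises eGFR in the arm that stays lighter, which is tirzepatide, so it is not conservative. It could look like a renal advantage or offset a small true decline. The trial has no data monitoring committee (SAP 4.8.1), and the study team's periodic review of the double-blind period is blinded (protocol 8.2.5). The SAP tables are therefore the main planned between-arm look at filtration. A second marker is already being measured, yet no estimate is planned from it.

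**Working it through.** **1. Schedule.** Counting the 27 visit columns of the Schedule of Activities:

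| Row | Visits |
|---|---|
| Chemistry (creatinine) | 1, 2, 5, 8, 11, 15, 18, 21, 24, ED, 801 |
| Cystatin C | 1, 11, 24, ED, 801 |
| UACR | 1, 11, 24, ED, 801 |

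In double-blind treatment creatinine is planned at Weeks 52, 64, 76 and 88, plus early discontinuation (ED). Cystatin C is planned at Week 88 or ED. Both have a Week 36 value.

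**2. The plan's own figure.** The only quantity given for the divergence is the sample-size assumption: 6%, SD 8%, dropout 25%, 300 per arm, 2-sided 0.05.
- Evaluable per arm: 300 × (1 − 0.25) = 225.
- Standard error: 8 × √(2/225) = 0.754. Then 6 / 0.754 = 7.96, and power exceeds 0.9999.

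The stated power of more than 90% is true as an inequality. It carries no renal information; the 6% is all that is used below.

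**3. Does the planned model remove the effect?** The default safety model in SAP 4.6 adjusts for country, sex, dose at randomization, weight-loss category at randomization and the baseline value. All are fixed by Week 36, so none can adjust for a difference that arises afterwards.

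**4. Possible size, by assumption only.** The documents give no body composition, no creatinine change and no expected eGFR difference. Let *r* be the relative deficit in creatinine generation on tirzepatide and *e* the creatinine exponent in the equation. Overstatement of eGFR = (1 − *r*)^(−*e*) − 1.

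Assumed: body weight 85 kg, lean mass 50 kg, generation proportional to lean mass, *e* either 1.2 or 0.3. Then *r* = 0.06 × 85 × share / 50.

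| Lean share of the weight difference | *r* | *e* = 1.2 | *e* = 0.3 |
|---|---|---|---|
| 0 | 0% | 0% | 0% |
| 0.10 | 1.02% | 1.24% | 0.31% |
| 0.25 | 2.55% | 3.15% | 0.78% |
| 0.40 | 4.08% | 5.13% | 1.26% |

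If generation fell by the full 6%, the results would be 7.7% and 1.9%. At an assumed eGFR of 90, the 0.40 row is 0.0513 × 90 = 4.6 or 0.0126 × 90 = 1.1 mL/min/1.73 m².

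**5. What that could and could not hide.** The bounded categories in the planned shift table are 15, 15 and 30 mL/min/1.73 m² wide, so a shift of up to about 4.6 moves only participants near a boundary. A mean comparison is more sensitive. With an assumed SD of change of 8 to 15 and 225 per arm, the standard error is 0.75 to 1.41. A shift of 4.6 is then 3.3 to 6.1 standard errors, and one of 1.1 is 0.8 to 1.5.

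**The case against.** **Renal safety is covered more widely than eGFR.** This is correct. A reader might infer that renal safety as a whole rests on creatinine eGFR. The documents do not support that: UACR, two renal event searches and a dehydration search are planned. None of them estimates filtration, however, so the gap in the eGFR comparison remains.

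**Cystatin C already has a route to analysis.** This stands in part. SAP 4.6.5.11 sends renal laboratory measures to 4.6.3.3, which covers other significant adverse events; the laboratory section is 4.6.3.6. Read as 4.6.3.6, cystatin C would get descriptive summaries by arm and a low/normal/high shift table. Its change baseline under Table GPHN.4.1 would normally be Week 36. Section 4.6.3.6 limits modelling to selected tests without naming them, and nothing converts cystatin C to eGFR.

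**The artefact does not match the stated danger.** A reader might infer that acute renal injury from dehydration could be masked. It could not: a shift of a few mL/min/1.73 m² does not conceal an acute fall, and cystatin C, drawn about once on double-blind treatment, would be worse than creatinine at catching a transient one.

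**The size is assumed, and the second marker is imperfect.** Both stand. Zero is inside the range, and cystatin C may vary with fat mass, which also differs between arms if the weight difference is partly fat. That argues for showing both estimates, not for showing only one.

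**Additional analyses are permitted anyway (SAP 4.1).** True, and no alpha depends on this. Naming the analysis in advance still avoids choosing the marker after seeing the creatinine result.

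**Conclusion.** The point holds in a limited form. The planned between-arm eGFR analyses are creatinine-only. A post-randomization weight difference of at least 6% is planned, and the model's covariates cannot remove its effect on creatinine. If part of that difference is lean tissue, creatinine eGFR would sit somewhat higher on tirzepatide and could understate a small, sustained decline.

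The size is about 0% to 5% (0 to 4.6 mL/min/1.73 m² at an eGFR of 90) under the illustrative lean shares of 0 to 0.40. It is at most about 1.3% with the smaller exponent. These figures rest on body weight, lean mass, lean share, exponent and proportionality assumptions that are not in the documents; only the 6% is documented.

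The plan would still show a large or acute fall, and nothing here indicates that renal harm is occurring. The sample size, power, alpha and efficacy analyses are unaffected.

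**What to change.** In SAP 4.6.5.11:

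1. Name the filtration marker and the CKD-EPI equation version behind the reported eGFR.
2. Correct the cross-reference from 4.6.3.3 to 4.6.3.6.
3. Add a sensitivity analysis with eGFR from cystatin C, or from creatinine plus cystatin C: an ANCOVA of change from Week 36 to Week 88 with the SAP 4.6 safety covariates, and a Week 36 to Week 88 category shift. Show the creatinine result beside it for the same participants and visits, and state how ED values are used.
4. Do not build a min-to-min table for cystatin C. With about one on-treatment value it would not be comparable with the creatinine table, which can draw on four scheduled values.
5. State the reading in advance. A creatinine eGFR advantage for tirzepatide that cystatin C does not show should not be read as renal benefit, or as excluding a small decline. A creatinine decline on tirzepatide should not be discounted: it runs against the artefact and is stronger evidence of harm.

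The cost is one derived variable and two displays from samples already scheduled. The drawback is that cystatin C may vary with fat mass, so neither estimate should be presented alone.
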